| Reference therapy | Historical response rates to chemotherapy in advanced cutaneous squamous cell carcinoma in transplant recipients (reference response rate 5-10%) |
| Statistical Methodology | 
Definition of primary outcome/endpoint: The primary endpoint is the overall response rate as defined as the best response, confirmed at ≥ 4 weeks, within the first 24 weeks of the start of study therapy, using RECIST v1.1 criteria.
 
Definition of secondary outcomes/endpoints: PFS is defined as time from registration to time of clinical or radiographic disease progression as defined by RECIST v1.1 criteria, or death. OS is defined as time from registration to time of death from any cause.
 
Analytic plan for primary objective: We will estimate the response rate to ruxolitinib using the exact 95% confidence interval based on the binomial distribution.
 
Analytic plan for secondary and exploratory objectives:
 
• We will estimate the survival distribution for both PFS and OS endpoints using the Kaplan Meier method. The log rank test will be used to examine differences between survival curves.• For correlative studies we will apply either the Fisher's exact test or Wilcoxon rank sum test to examine the correlation between response status and markers for categorical and continuous variables, respectively. 
Sample size justification: We will utilize a Simon mini-max two-stage design in which a 5% RR is considered not promising, a 20% RR is considered promising, and the probabilities of a type I error (falsely accepting a non-promising therapy) and type II error (falsely rejecting a promising therapy) are set at 0.10 and 0.10, respectively. Eighteen patients with advanced cSCC will be accrued in the first stage. If 1 or more patients achieve a response, then an additional 14 will be accrued. If 4 or fewer responses are seen, the study will be declared negative.
 |

Protocol Schema:

[figure not shown]

Table of Contents

| | | |
|-----|---|----|
| 1. | Protocol Signature Page | 3 |
| 1. | Introduction..... | 12 |
| 2. | Study Objectives | 12 |
| 2.1 | Primary Objective | 12 |
| 2.2 | Secondary Objectives..... | 12 |
| 2.3 | Exploratory Objectives | 13 |
| 3. | Background | 13 |
| 3.1 | Cutaneous Squamous Cell Carcinoma | 13 |
| 3.2 | Rationale for JAK inhibition in advanced cutaneous squamous cell carcinoma..... | 13 |

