Correlative studies: A minimum of 10 enrolled subjects must undergo paired biopsies for correlative studies. CT-guided biopsies will be collected at baseline and between C2D1 and C2D8 of therapy for correlative studies. A biopsy at the time of disease progression is optional in all subjects. Subjects in whom a biopsy is technically not feasible or in whom would result in unacceptable risk, in the opinion of the investigator, may be exempted from the biopsy requirement with discussion with the principal investigator.

Whole blood will be requested as outlined in section 13.2 for peripheral blood mononuclear cell (PBMC) and circulating tumor DNA (ctDNA) collection to evaluate the effect of ruxolitinib on circulating immune cell populations before and during treatment and to further evaluate ctDNA as a potential biomarker of disease response.

Duration of follow-up: Adverse events and laboratory tests will be graded using the NCI CTCAE v5.0 scoring system. Adverse events will be assessed continuously during the study and for **90 days** after the last dose of treatment. Subjects will be followed for at least **90 days** post-study, or until all treatment related adverse events have recovered to baseline or are deemed irreversible by the investigator. Subjects who are removed from study for reasons other than progression of disease will be followed every 3 months with imaging to evaluate disease status and survival analysis while the study remains open.

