5.3.2 Blood Collection

Whole blood will be requested as outlined in section 13.2 for peripheral blood mononuclear cell (PBMC) and circulating tumor DNA (ctDNA) collection to evaluate the effect of ruxolitinib on circulating immune cell populations before and during treatment and to further evaluate ctDNA as a potential biomarker of disease response.

Detailed specimen processing and shipping information can be found in the laboratory manual.

Correlative analysis may include some or all of the following studies:

- IHC and/or Western blot and qRT-PCR to evaluate changes in STAT3, Cyclin D1, and other proteins
- Multiplex immunohistochemistry to assess changes in the immune microenvironment
- Bulk and single cell RNA-Seq analysis may be performed on paired tumor biopsies to assess mechanisms of disease response and resistance
- Additional studies may be performed in the future.

Samples will be stored on-site and shipments will be sent to the [name] laboratory by batch shipments when requested to the address listed below:

[name] Laboratory
Columbia University Medical Center
[name]
[name]
[name]

The analyzing laboratories will be notified by email ([contact]) the day the samples are sent. The email will contain the following information:

- Subject ID

- Subject Initials
- Date of collection
- Time point (e.g. baseline, cycle 2 day 1, end of treatment, etc)
- Name of study center
- Shipment date
- Contents of shipment

Samples should be shipped via courier so that the package is tracked appropriately (specifically Federal Express or UPS). The samples should be shipped for morning delivery, Monday through Thursday for optimal processing.

Samples will be tracked through a Microsoft Excel tracker.

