17. STATISTICAL CONSIDERATIONS

17.1 Study Design and Sample Size

This is a multi-center, non-randomized, open-label phase 2 trial to evaluate the efficacy and safety of ruxolitinib in post-transplant patients with advanced cutaneous squamous cell carcinoma. The primary endpoint is overall response rate, defined as the best response confirmed

within the 24 weeks of the start of study therapy.

We will use a Simon Two-Stage Min-Max design with a target overall response rate of 20% (alternative hypothesis), compared to a historical response rate of 5% (null hypothesis) with chemotherapy, with one-sided probability of a type I error set at 0.10 and power of 90%. In the first stage, 18 patients will be accrued. If less than 1 patient achieves a response among the initial 18 patients, the study will be declared negative and terminated. If at least 1 patient achieves a response, an additional 14 patients will be accrued to the second stage for a total of 32 evaluable patients. Overall, if 4 or fewer responses are seen, the study will be declared negative. If at least 5 total patients achieve a response, that treatment will be declared positive for attaining the primary endpoint. There is a 40% chance of stopping at Stage 1 if the true confirmed response rate is at most 5% (null hypothesis). Accounting for 10% dropout, we will plan to enroll a total of 35 patients unless a second safety lead-in is required, in which case the the maximum potential accrual will be 41 patients.

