17.2 Study Endpoints and Analytic Plan

All subjects who receive at least one dose of study drug will be considered evaluable and included in the efficacy and safety analysis.

Definition of primary outcome/endpoint:

The primary endpoint is the overall response rate defined as the best response within the first 24 weeks of the start of study therapy using RECIST v. 1.1 that has been confirmed at a subsequent time point (≥ 4 weeks).

Definition of secondary outcomes/endpoints:

PFS is defined as time from enrollment to time of clinical or radiographic disease progression as defined by RECIST v.1.1 criteria. OS is defined as time from enrollment to time of death from any cause.

Analytic plan for primary objective:

The overall response rate will be summarized using point estimates and 95% confidence intervals.

Analytic plan for secondary and exploratory objectives:

- We will estimate the survival distribution for both PFS and OS endpoints using the Kaplan Meier method. The log rank test will be used to examine differences between survival curves using prognostic markers.
- For correlative studies we will apply either the Fisher's exact test or Wilcoxon Rank Sum test to examine the associations between response status and changes in markers expression for categorical and continuous variables, respectively. Because of the limited sample size, the biomarker data analysis is for exploratory research only.
- Toxicity data will be summarized by type, frequency, and severity according to the NCI CTCAE criteria v4.0.

- Pharmacokinetic and pharmacodynamic parameters will be summarized using descriptive statistics and graphical methods (individual profile plots).

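### For PFS and OS the plan names only the log-rank test, so any continuous marker would have to be split at an unstated cut-point; a Cox score test on the continuous marker usually keeps more power

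*Combined protocol and SAP*

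**What the plan says.** Section 17.2 estimates PFS and OS by Kaplan-Meier and adds: "The log rank test will be used to examine differences between survival curves using prognostic markers". The synopsis (Statistical Methodology) is shorter still: "The log rank test will be used to examine differences between survival curves". Neither place lists the markers or gives a grouping rule. No Cox model or trend test appears anywhere in the document.

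The next bullet of 17.2 does distinguish data types, but only for response. It assigns Fisher's exact test and the Wilcoxon rank sum test to "associations between response status and changes in markers expression for categorical and continuous variables, respectively". It then adds: "Because of the limited sample size, the biomarker data analysis is for exploratory research only".

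The planned assays, listed in section 5.3.2, include "IHC and/or Western blot and qRT-PCR to evaluate changes in STAT3, Cyclin D1, and other proteins". The same section plans blood work on circulating immune cells and ctDNA. Section 2.3 makes the link between clinical benefit or response and change in pSTAT3 and cyclin D1 an exploratory objective, and section 2.2 measures clinical benefit by PFS and OS.

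On numbers, section 5.1 says: "A minimum of 10 enrolled subjects must undergo paired biopsies for correlative studies". Section 17.1 says: "an additional 14 patients will be accrued to the second stage for a total of 32 evaluable patients". It also says: "Accounting for 10% dropout, we will plan to enroll a total of 35 patients".

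**The concern.** The log-rank test compares groups. The trial has a single arm and no stratification factors (sections 8.4 and 17.4), so the groups must come from the markers. Protein expression, cell counts and ctDNA level are largely quantitative. An analyst who applies 17.2 to such a marker has to dichotomise it, and the plan does not say where.

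Two things are at stake. A split discards information in a trial that has little to spare. An unfixed split also leaves room, intended or not, to choose the cut after seeing the outcome, and a p-value from such a choice cannot be read at face value.

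**Working it through.** **Inputs from the documents.** There are 18 + 14 = 32 evaluable patients, 35 planned (41 with a second safety lead-in), and at least 10 with paired biopsies. Section 13.2 schedules research blood with no subset limit. The Introduction gives a 3-year median survival after diagnosis of metastasis. The plan states no power, alpha, event count, hazard ratio or cut-point for this analysis, so there is no figure of its own to reproduce.

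**Assumptions not in the documents.** Two-sided 5% test; normally distributed marker; log-linear effect with hazard ratio (HR) 1.5 to 2 per SD; exponential times. For PFS, a 4-month median with censoring between 12 and 36 months (about 93-96% events). For OS, the 3-year median applied from enrolment with the same censoring (about 38-39% events). Fixed censoring of 20% and 50% was also tried.

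**Step 1: information kept by a split.** For a normal marker, the squared correlation with its median-split indicator is 2/π = 0.637. At the upper quartile it is 0.539.

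**Step 2: approximate power.** Power ≈ Φ(√(D·V)·ln HR − 1.96), where D is the number of events, V = 1 for the Cox score test and V = 0.637 for the median split. With D = 25 and HR 2:

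- Cox score: 5 × 0.693 − 1.96 = 1.51, power 93%.
- Median split: √(25 × 0.637) × 0.693 − 1.96 = 0.81, power 79%.

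This formula is optimistic for so few events, so the results below come from simulation.

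**Step 3: simulated power, Cox score against median-split log-rank.**

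| n | Setting | HR 1.5 per SD | HR 2 per SD |
|---|---|---|---|
| 32 | PFS, 4-month median | 53% vs 37% | 90% vs 72% |
| 32 | 20% censored | 47% vs 32% | 86% vs 66% |
| 32 | 50% censored | 33% vs 22% | 71% vs 49% |
| 32 | OS, 3-year median | 28% vs 19% | 61% vs 41% |
| 10 | PFS, 4-month median | 19% vs 14% | 37% vs 26% |
| 10 | 20% censored | 16% vs 13% | 32% vs 23% |
| 10 | OS, 3-year median | 11% vs 9% | 21% vs 15% |

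With all 35 patients, 20% censoring and HR 2, the figures are 89% against 71%. At n = 10 a large gain appears only for very strong effects: at HR 3 per SD for PFS, with permutation p-values, it is 59% against 32%.

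**Step 4: false positives with no marker effect.** At n = 32 a fixed median split rejects 5-6% of the time and the Cox score test about 5%. Taking the best of seven cuts between the 20th and 80th percentiles gives 21-23% at n = 32 and 29-33% at n = 10. Searching every cut in that range gives about 30% and 35%. At n = 10, permutation p-values hold the level for both tests (4.7%).

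**Step 5: a different effect shape.** Suppose the hazard doubles at a step, with n = 32 and PFS as above. If the step is at the sample median, the log-rank test wins by 48% to 31%. If it is at the population median, so that the sample split misplaces some patients, it still wins by 36% to 30%.

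**The case against.** The strongest reply is that 17.2 nowhere says these markers are continuous. Prognostic markers could mean categorical baseline factors, for which the log-rank test is right; there it is itself the Cox score test, so nothing is lost. The correlative markers have their own bullet, which matches test to data type. This stands as a limit. A reader might infer that the plan commits to dichotomising pSTAT3, cyclin D1 or ctDNA, and the text does not go that far. What remains is that sections 2.2 and 2.3 call for relating marker change to clinical benefit measured by PFS and OS, and the only method offered for those endpoints needs groups.

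Second, the plan labels the biomarker work exploratory and sets no alpha for it. A reader might infer that it invites a cut-point search. It proposes none, so the 20-35% describes what an open choice permits, not what the plan says will happen. Fixing a median split in advance would close that door equally well, at the cost in power shown above.

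Third, a reader might infer that the Cox test is always stronger. Step 5 shows otherwise. Nor is the gain large in the biopsy subset at moderate effects, where neither test is of much use. Ten is, however, a minimum: section 5.3.1 makes later biopsies optional rather than excluded.

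**Conclusion.** The concern holds in limited form. The plan gives no method for relating a continuous marker to PFS or OS without a split, and no rule for the split. If such markers are tested and the effect is roughly log-linear, the Cox score test gains about 9 to 22 percentage points of power at n = 32 over the settings tried for HR 1.5 to 2 per SD. At n = 10 the gain is about 2 to 11 points. The benefit therefore lies mainly in blood markers collected in all patients, where n can reach 35 or more.

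The absolute powers depend on the assumed medians and censoring. The direction held in every log-linear setting tried and reversed for a step at the median. This is a low-priority improvement to an exploratory analysis, with no bearing on the response-rate decision.

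**What to change.** In section 17.2 and the synopsis:

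- List the markers to be related to PFS and OS, and state which are continuous.
- For continuous markers, use a Cox score test with the marker entered as continuous, on a scale (raw or log) fixed in advance for each marker. Leaving the scale to be chosen after inspection would reopen an analyst choice.
- Use a permutation p-value in the biopsy subset of roughly 10 patients.
- Report the hazard ratio per SD with its confidence interval.
- Keep the log-rank test for markers that are categorical by nature.
- Show Kaplan-Meier curves by median split for display only.
- Keep the exploratory label.

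The cost is wording only: no extra patients, samples or visits. The downside is the reliance on a roughly monotone, log-linear effect, with some loss of power if the true effect is a step at the median.

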2.3 Exploratory Objectives

- To explore the association between clinical benefit/response and changes in expression of phosphorylated STAT3 and Cyclin D1 using pre- and post-treatment tumor biopsies.
- To explore the effect of ruxolitinib on the tumor immune microenvironment
- To explore the effect of ruxolitinib on circulating immune cell populations
- To explore mechanisms of sensitivity and resistance using RNA-Seq analysis of tumor biopsies from responding and non-responding patients.

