5.3 Correlative Studies

5.3.1 Tumor biopsies for pharmacodynamic assessment

The biological activity of ruxolitinib will be assessed by performing paired tumor biopsies

at baseline, and between Cycle 2 Day 1 and Cycle 2, Day 8 of study therapy. These biopsies will be mandatory in the first 10 patients enrolled on Stage I of the study (first 18 enrolled subjects), and optional in subsequent patients. A biopsy at the time of disease progression is optional in all patients. (Note: If sufficient flash frozen tumor material is available from a prior tumor biopsy performed within 3 months of registration with no intervening therapy, then a repeat baseline biopsy will not be necessary.)

A goal of at least 3 cores and up to 8 cores from the patient's tumor biopsy specimen, if safe to obtain, will be obtained for research purposes. The first core will be placed in buffered formalin and paraffin-embedded as standard of care. Subsequent cores will be flash frozen.

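### Marker change is tested only against responder status in as few as 10 biopsied patients; a rank correlation with percent tumor change would use the same data better

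*Combined protocol and SAP*

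**What the plan says.** The first exploratory objective (Section 2.3) is "To explore the association between clinical benefit/response and changes in expression of phosphorylated STAT3 and Cyclin D1", using tumor biopsies taken before and during treatment. For the analysis, Section 17.2 names Fisher's exact test for categorical markers and the Wilcoxon rank sum test for continuous ones, to "examine the associations between response status and changes in markers expression for categorical and continuous variables". It adds: "Because of the limited sample size, the biomarker data analysis is for exploratory research only". No significance level, power or effect size is given for this analysis.

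On numbers, Section 5.1 states: "A minimum of 10 enrolled subjects must undergo paired biopsies for correlative studies". Section 5.3.1 states: "These biopsies will be mandatory in the first 10 patients enrolled on Stage I of the study (first 18 enrolled subjects), and optional in subsequent" enrollees. Exemptions are allowed where a biopsy is not feasible or too risky.

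On tumor size, Section 15.3 has the sum of target-lesion diameters recorded at baseline. The study calendar repeats tumor measurements every other cycle, and Section 15.5.1 defines partial response as a fall of at least 30% in that sum. No planned analysis uses the percent change itself.

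**The concern.** Section 3.4 states the hypothesis that inhibition of STAT3 and cyclin D1 will go along with response. The only test in 17.2 that links marker change to tumor response first reduces each patient's tumor change to responder or non-responder. In a set of about 10 patients with a low response rate, one of the two groups may hold nobody or one person. All ordering among non-responders, from slight shrinkage to rapid growth, is discarded, although the objective speaks of clinical benefit as well as response.

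At stake is how much this exploratory analysis can learn from the paired tissue. The primary endpoint and the go/no-go decision are not affected.

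**Working it through.** **Plan's own figure.** There is none to reproduce for the marker analysis. Section 17.1 gives "one-sided probability of a type I error set at 0.10 and power of 90"%, but for the primary endpoint only.

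**Inputs from the documents.** Biopsied patients n = 10 as the minimum (5.1, 5.3.1). Response rates from 17.1: "target overall response rate of 20% (alternative hypothesis), compared to a historical response rate of 5% (null hypothesis"). The synopsis gives a "reference response rate 5-10"% for chemotherapy, so 5%, 10% and 20% are used.

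**Assumed.** Two-sided 0.05; bivariate normal marker change and percent tumor change; true correlation ρ of 0.5 to 0.7; response defined as the best p% of percent change.

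**Step 1: number of responders among 10.** P(0) = (1−p)^10 and P(1) = 10p(1−p)^9.

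| Response rate | P(0) | P(1) | P(0 or 1) | Expected responders |
|---|---|---|---|---|
| 5% | 0.599 | 0.315 | 0.914 | 0.5 |
| 10% | 0.349 | 0.387 | 0.736 | 1 |
| 20% | 0.107 | 0.268 | 0.376 | 2 |

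**Step 2: smallest attainable p.** With k responders among 10, the smallest exact two-sided Wilcoxon p is 2/C(10,k):

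- k = 0: no test exists.
- k = 1: 2/10 = 0.20.
- k = 2: 2/45 = 0.044, only if the marker changes separate completely.
- k = 3: 2/120 = 0.017.

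At a 20% rate P(exactly 2) = 45 × 0.2² × 0.8⁸ = 0.302, so P(2 or fewer) = 0.376 + 0.302 = 0.678. In about two samples of three the test is impossible, cannot reach 0.05, or needs complete separation.

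Fisher's test with a marker split 5/5 has a best p of 0.44 with 2 responders and 0.17 with 3. With 1 responder its best possible p is 0.10, when that patient is the only one marker-positive.

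**Step 3: power with the outcome kept continuous.** Percent change = 100 × (sum at scan − baseline sum) / baseline sum. Simulation with 40,000 samples per setting, n = 10, 20% response rate, exact Wilcoxon against Spearman with a permutation critical value:

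| ρ | Wilcoxon by response | Spearman on percent change |
|---|---|---|
| 0.5 | 10% | 27% |
| 0.6 | 14% | 39% |
| 0.7 | 21% | 56% |

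The ratio is 2.6 to 2.7 here, and 2.2 to 2.7 over ρ from 0.3 to 0.9.

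**Step 4: how far the gain moves.**

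- Lower response rates, n = 10: the ratio is about 5 to 6 at 10% and 14 to 17 at 5%, because Wilcoxon power almost vanishes.
- 18 biopsied patients at a 20% rate: P(0 or 1) = 0.8^18 + 18 × 0.2 × 0.8^17 = 0.018 + 0.081 = 0.099, and the ratio is 1.3 to 2.1.
- Two-sided 0.10, n = 10, 20% rate: 16% against 39%, 22% against 53%, and 30% against 69% at ρ = 0.5, 0.6 and 0.7.
- Two of 10 patients without a follow-up scan, lost at random: Spearman on 8 has 19%, 28% and 41%, about twice the Wilcoxon figures for 10.

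**Step 5: who would lack a percent change.** The on-treatment biopsy falls between Cycle 2 Day 1 and Day 8, which is study days 29 to 36 with 28-day cycles. The first scan is at week 8. A patient with a marker change but no percent change must therefore have left assessment in the few weeks between. Such patients may be few, but they are likely to be early failures. Section 17.5.2 counts unassessable patients and early deaths as treatment failures, so a correlation that drops them would be selective.

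**The case against.** **The plan already limits its claim.** It says "Because of the limited sample size, the biomarker data analysis is for exploratory research only", sets no significance level and attaches no decision to the result. This stands and keeps the point minor. But a limited sample is a reason to prefer the more efficient method, and the label does not favor the weaker one.

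**Ten is a floor.** Later patients may volunteer, and inclusion criterion 12 in Section 6.1 asks subjects in general to agree to biopsies. Correlative blood samples are not limited to 10 patients. This stands: with 18 biopsied patients the gain is about twofold or less.

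**Other analyses need no responders.** Section 17.2 also plans log-rank comparisons of PFS and OS by prognostic markers. This stands, but they do not relate marker change to tumor shrinkage.

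**The size rests on assumptions.** The correlations are not in the documents, and the simulation ignores confirmation of response, new lesions and non-target progression. This stands. The binomial figures and the smallest p-values do not depend on it.

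**Percent change has its own gaps.** It misses progression by new or non-target lesions and does not exist without a follow-up scan. A reader might infer that the switch is free. It needs no new data, but it does need a ranking rule.

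**The biopsies have other uses.** A reader might infer that this test is what justifies them. The documents do not support that: Section 5.3.1 presents them as pharmacodynamic assessment, a secondary objective summarized descriptively with individual profile plots, and Section 2.3 adds immune-microenvironment and RNA-Seq objectives.

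**Conclusion.** The point holds as an improvement to an exploratory analysis. With 10 biopsied patients, the chance that the Wilcoxon test is impossible or cannot give p below 0.20 is 38% at the target rate and 74 to 91% at the reference rates. A reader might infer that one or no responder is likely in any case; at 20% it is not, since 62% of samples would have at least two.

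At a 20% rate with n = 10, the rank correlation has roughly 2.5 times the power, given bivariate normality and ρ of 0.5 to 0.7. That multiple should not be carried to other settings: it is larger at lower response rates and about 2 or less with 18 patients. Absolute power stays modest at 27 to 56%, so a null result would remain weak evidence. The simulated figures do not include the ranking rule proposed below.

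**What to change.** In Section 17.2:

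- Make the Spearman correlation of marker change with best percent change in the sum of target diameters the main exploratory marker-response analysis. State the window (the 24 weeks of the primary endpoint would match it) and use a permutation p-value, because the rule below creates ties.
- Keep the comparison of responders with non-responders as description.
- Assign the worst rank to patients with no post-baseline scan because of early death or progression, and to those whose best response is progression by new or non-target lesions. Add a sensitivity analysis that excludes them.

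The cost is SAP wording, a ranking convention and a little more analysis. No visit, scan, biopsy or data item is added, and the primary endpoint and sample size are unchanged.
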